6.4 Administration of Prior TPO-RA

Descriptive statistics of variables related to the administration of prior TPO-RA will be displayed for all enrolled subjects. The table will be divided in 2 sections (one for romiplostim and one for eltrombopag) and include a summary of:

- Duration of prior treatment with romiplostim and eltrombopag (weeks) as a continuous variable
- Most recent dose level of eltrombopag and romiplostim (mg or mcg/kg) as a categorical variable

- Subject-reported responses to the 3 brief questions in the romiplostim and eltrombopag eCRF pages

An additional table will be created comparing the most recent dose level of prior TPO-RA (romiplostim and eltrombopag) recorded at the Baseline Visit to the stable dose of avatrombopag at the end of study. The stable dose of avatrombopag at the end of the study will be defined as the final avatrombopag dose recorded in the eCRF at the End of Study Visit on Day 90. The prior TPO-RA dose will be categorized into 3 dose groups (low, medium, and high), and the table will summarize the stable dose of avatrombopag by prior TPO-RA within each group.

Listings (one for romiplostim and one for eltrombopag) will present each individual subject's duration of prior treatment, most recent dose level (units), date of last dose, and answers to the 3 questions in the romiplostim and eltrombopag eCRF pages.

7. Prior and Concomitant Treatment

Prior and Concomitant medications will be classified according to the World Health Organization (WHO) Drug Dictionary Global (Enhanced w/WHO Herbal Dictionary). The coding version may be updated prior to database lock if a newer version is available. Medications will be coded per the Anatomical Therapeutic Classification (ATC). All medications will be documented from the time of informed consent up to the End of Study/Early Termination Visit.

Prior medications are those which start and stop before the first day of study treatment. Concomitant medications are those which are being taken on or after the first day of study treatment.

Tabular summaries will display the number and percentage of subjects with at least one medication in ATC Level 2 and preferred name categories by prior TPO-RA (romiplostim and eltrombopag) and overall groups. Subjects who have taken a medication more than once will only be summarized once per ATC Level 2 or preferred name.

The tabular summaries to be provided are as follows:

- Prior Medications
- Concomitant Medications
- Concomitant Medications taken as rescue for a bleeding event

An overall listing of medications will be provided. The listing will designate whether a medication is considered prior or concomitant. A separate listing will also be produced for concomitant medications taken as rescue for a bleeding event.

An overall listing of procedures will also be provided with procedure name, start and end dates, a flag for prior/concomitant procedure, and details about reason for the procedure (indication).

8. Efficacy/Effectiveness Evaluation

8.1 Treatment Satisfaction Questionnaire for Medication (TSQM)

Confidential

The domain scores of effectiveness, side effects, convenience, and global satisfaction will be computed according to the Treatment Satisfaction Questionnaire for Medication (TSQM) User Manual (IQVIA, Version 1.6: 04 March 2020). Each domain score ranges from 0 to 100, and a higher score indicates a better outcome. The TSQM will be administered at Baseline (before the first dose of avatrombopag), Day 30, and Day 90.

The scoring algorithms are as follows:

If more than one item score is missing, the scale score should not be computed and set to missing. If a subject answers "No" to Item 4, the side effects scale score will not be computed.

Effectiveness

Effectiveness scale score = $[(\text{Item 1} + \text{Item 2} + \text{Item 3} - 3)/18] \times 100$

If one item is missing:

Effectiveness scale score = $[(\text{Item 1?} + \text{Item 2?} + \text{Item 3?} - 2)/12] \times 100$

Side Effects

If Question 4 is answered 'No' then score = 100

Else:

Side effects scale score = $[(\text{Item 5} + \text{Item 6} + \text{Item 7} + \text{Item 8} - 4)/16] \times 100$

If one item is missing:

Side effects scale score = $[(\text{Item 5?} + \text{Item 6?} + \text{Item 7?} + \text{Item 8?} - 3)/12] \times 100$

Convenience

Convenience scale score = $[(\text{Item 9} + \text{Item 10} + \text{Item 11} - 3)/18] \times 100$

If one item is missing:

Convenience scale score = $[(\text{Item 9?} + \text{Item 10?} + \text{Item 11?} - 2)/12] \times 100$

Global Satisfaction

Global satisfaction scale score = $[(\text{Item 12} + \text{Item 13} + \text{Item 14} - 3)/14] \times 100$

If Item 12 or 13 is missing

$([(\text{Sum(the two completed items)}) - 2] \text{ divided by } 10) * 100$

If Item 14 is missing

$([(\text{Sum(Item 12 and Item 13)}) - 2] \text{ divided by } 8) * 100$

Descriptive statistics will be summarized for each domain score and each visit. The change from Baseline and percent change in each mean domain score will be

Confidential

summarized descriptively by prior TPO-RA (eltrombopag vs romiplostim) and overall.

The primary interest in the TSQM assessment is the convenience domain score. The hypothesis is that switching from a prior TPO-RA treatment (e.g., eltrombopag or romiplostim) to avatrombopag results in an improvement in the convenience domain score. Change from Baseline to Day 90 (or End of Study) in the convenience domain score will be tested using paired t-tests, by prior TPO-RA treatment (eltrombopag vs romiplostim) and overall. As a part of the secondary endpoint analyses, this paired t-test analysis will also be performed to examine the global satisfaction, effectiveness, and side effects domain score by prior TPO-RA treatment (eltrombopag vs romiplostim) and overall.

A listing of TSQM scores will be provided.

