10.2.3 Analysis of the Treatment Satisfaction Questionnaire for Medication

Domain scores of effectiveness, side effects, convenience, and global satisfaction will be computed according to the TSQM manual, Version 1.4. Each domain score ranges from 0 to 100, and a higher score indicates a better outcome. Descriptive statistics will be summarized for each domain score and each visit. The change from Baseline and percent change in each mean domain score will be summarized descriptively.

The primary interest in the TSQM assessment is the convenience domain score. The hypothesis is that switching from a prior TPO-RA treatment (e.g., eltrombopag or romiplostim) to avatrombopag results in an improvement in the convenience domain score. Change from Baseline to Day 90 (or End of Study) in the convenience domain score will be tested using paired t-tests, by prior TPO-RA treatment (eltrombopag vs romiplostim) and overall.

Additional analyses on platelet count and TSQM may be conducted as appropriate.

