3.2.2 Secondary Endpoints

Change from Baseline in each of the 4 domains of the TSQM Version 1.4 (e.g., convenience, global satisfaction, effectiveness, and side effects) to Day 90 or End of Study.

Proportion of subjects who have a platelet count between $\geq 50 \times 10^9/L$ to $\leq 200 \times 10^9/L$ at Day 15, Day 30, Day 60, and Day 90.

Confidential

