4.3.4 Handling Missing Data

All available data will be included in data listings and tabulations.

No imputation of missing data is planned for study endpoints.

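### SAP 8.1 scores a subject with no side effects both as not computed and as 100, so the TSQM side-effects endpoint has no single definition

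*SAP*

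**What the plan says.** SAP Section 3.2.2 makes this a secondary endpoint: "Change from Baseline in each of the 4 domains of the TSQM Version 1.4". Side effects is one of the four domains.

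SAP Section 8.1 then gives the scoring. The opening paragraph has a general missing-item rule: "If more than one item score is missing, the scale score should not be computed and set to missing". The next sentence deals with a No to Item 4 and says "the side effects scale score will not be computed". Further down, the block headed Side Effects opens with "If Question 4 is answered 'No' then score = 100" and applies the Items 5 to 8 formula otherwise.

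On analysis, Section 8.1 says "this paired t-test analysis will also be performed to examine the global satisfaction, effectiveness, and side effects domain score", separately by prior TPO-RA and overall. SAP Section 4.3.4 adds "No imputation of missing data is planned for study endpoints".

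Protocol Section 10.2.3 has no rule for Item 4. It sets the scale ("Each domain score ranges from 0 to 100, and a higher score indicates a better outcome") and refers to the TSQM manual.

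**The concern.** The same questionnaire answer leads to no value under one line and to the best possible value under the other. A production programmer and an independent validator could each follow the SAP and build different datasets.

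The choice matters because the not-computed rule selects on the outcome. A change score would exist only for subjects reporting side effects at both visits. A subject whose side effects went away after the switch (the benefit) and one who developed them (the harm) would both leave the analysis. The by-visit descriptive statistics for this domain would also describe only subjects with side effects. Because the study is open-label, an unresolved rule could end up being chosen with the data in view.

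**Working it through.** **1. Plan's own figure.** The plan states no power or sample-size figure for side effects. Its only design calculation is for convenience (SAP 3.4): n = 50, change 8, SD 19, two-sided alpha 0.05, power 83%. Taking 19 as the SD of the change, the noncentral t with 49 df and noncentrality 8/19 × √50 = 2.98 gives 83.1%, which agrees. This figure does not depend on the Item 4 rule.

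**2. The two rules.** Call them A (not computed, hence missing) and B (score 100). The side-effects formula is (sum of Items 5 to 8 − 4)/16 × 100. With the best answer (5) on all four items it gives (20 − 4)/16 × 100 = 100, so B puts a No at the top of the scale.

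| Baseline → Day 90 | Change under A | Change under B |
|---|---|---|
| No → No | dropped | 0 |
| Yes → No (resolved) | dropped | 100 − Baseline score |
| No → Yes (new) | dropped | Day 90 score − 100 |
| Yes → Yes | difference of scores | difference of scores |

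**3. Worked example (assumed data, n = 50).** Suppose 25 No/No; 12 resolved from a score of 62.5 (change +37.5 each); 3 new, falling to 62.5 (−37.5 each); and 10 Yes/Yes with mean change 0.

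- Rule A: n = 10, mean change 0.0, p = 1.00.
- Rule B: mean = (12 × 37.5 − 3 × 37.5 + 0)/50 = 337.5/50 = +6.75; SD 20.2; t = 6.75/(20.2/√50) = 2.36; p = 0.022.

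**4. Range of assumptions.** The documents do not give the share answering No, or the mean or SD of the side-effects score. Let p0 and p1 be the No shares at Baseline and Day 90, m the mean among reporters at both visits, and φ the correlation between the two No answers. Then:

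- expected pairs kept under A = 50 × [(1 − p0)(1 − p1) + φ√(p0(1 − p0)p1(1 − p1))]
- expected mean change under B = (p1 − p0)(100 − m)

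For p0 = 0.5, p1 = 0.7, φ = 0.3 and m = 60, these give 50 × (0.15 + 0.3 × 0.229) = 10.9 pairs, and 0.2 × 40 = +8.0.

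Simulation with m = 60, SD 20, within-subject correlation 0.5, φ = 0.3 and no true change among persistent reporters:

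| No share, Baseline → Day 90 | A: pairs of 50 | A: mean change | A: rejects | B: mean change (n = 50) | B: rejects |
|---|---|---|---|---|---|
| 30% → 50% | 21 | about 0 | 6% | +8.0 | 50% |
| 50% → 70% | 11 | about 0 | 5% | +8.0 | 53% |
| 70% → 90% | 4 | about 0 | 5% | +8.1 | 76% |
| 50% → 50% | 16 | about 0 | 5% | about 0 | 5% |
| 70% → 70% | 8 | about 0 | 5% | about 0 | 5% |
| 80% → 80% | 4 | about 0 | 6% | about 0 | 5% |

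The Rule A rejection rates count only simulated trials with at least three pairs left.

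A second simulation used m = 65, SD 20 and a latent correlation of 0.3 between the No answers:

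- 60% → 80%: about 6 of 50 pairs and about 0 under A; +7.1 under B.
- 40% → 60%: about 14 pairs and about 0; +7.1.
- 80% → 60% (worsening): about 6 pairs and about 0; −7.1.
- 10% → 20%: about 37 pairs and about 0; +3.5.

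**The case against.** The strongest reply is that the lines can be reconciled. The general sentence says only that the score is not computed; unlike the sentence before it, it does not add that the score is set to missing. The side-effects block is an explicit if/else. Together they could mean that the score is not calculated from Items 5 to 8 but assigned 100, a reading that gives every line a function. Assigning 100 would then be scoring, not imputation, and SAP 4.3.4 would not apply. This reading is possible, but the SAP does not state it, and the adjacent sentence ties not computing a score to setting it missing. The ambiguity remains.

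The second objection concerns size, and it largely stands. The +7 to +8 is essentially the assumed shift in No times the assumed gap from 100, and the zero under Rule A follows from assuming no change among persistent reporters. With a stable No share, the two rules agree on the mean change. What does not depend on a shift is the loss of pairs.

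The third concerns scope. One of four domains is affected, and its t-test appears in the SAP but not in Protocol 10.2.3. Tolerability is also described by the adverse event tables. That limits the reach of the problem but does not give the endpoint a definition.

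**Conclusion.** The concern holds. The current SAP text gives two incompatible scores for the same answer, and nothing in either document resolves them. The number analysed and the by-visit summaries differ as soon as anyone answers No. The mean change and p-value differ materially when the No share moves between visits: under the assumptions shown, about 0 against +7 to +8 for a 20-point rise, and about 0 against −7 for a 20-point fall. They need not differ when the share is stable. These sizes are illustrations, because the documents give no No rates or side-effects score distribution. A secondary endpoint with planned tests in each prior TPO-RA group and overall should not be left in this state. The problem is confined to the side-effects domain; convenience, effectiveness, global satisfaction, the sample size and the primary AE/SAE endpoint are untouched.

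**What to change.** Check the user manual cited in SAP 8.1 (Version 1.6) and keep one rule for a No to Item 4. On the SAP's own text, the rule in the side-effects algorithm (No = 100) is the one to keep, subject to that check, because it retains the subjects whose status changed. Delete the conflicting sentence from the general paragraph. Protocol 10.2.3 attaches Version 1.4 to its manual reference, so state explicitly which manual governs scoring.

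Apply the rule identically at Baseline, Day 30 and Day 90/End of Study, in tables, t-tests and listings. Report the number answering No at each visit by prior TPO-RA and overall; the other rule can be shown as a sensitivity analysis.

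The cost is a one-sentence SAP edit and a small addition to the table shells. It needs no new data and places no burden on subjects. It should be made before database lock, the point by which Protocol Section 10 requires the SAP to be final.

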8.2 Analysis of Platelet Count

Platelet count (local lab) assessed at Baseline, Day 15, Day 30, Day 60, and Day 90 will be summarized descriptively for all enrolled subjects. A graphical presentation of platelet count over time will be provided by prior TPO-RA (romiplostim and eltrombopag) and overall.

The proportion of subjects who have a platelet count $\geq 50 \times 10^9/L$ and $\leq 200 \times 10^9/L$ will be tabulated using count and percentage for Baseline, Day 15, Day 30, Day 60, and Day 90.

A listing will provide details of local lab platelet counts by visit.

9. Safety Evaluation

Safety and tolerability will be assessed by examining exposure, treatment compliance, and adverse events by prior TPO-RA (romiplostim and eltrombopag) and overall of all enrolled subjects.

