1 INTRODUCTION AND BACKGROUND INFORMATION

1.1 Thrombocytopenia

Platelets originate from megakaryocytes in the bone marrow and are an important component of blood that function to maintain normal hemostasis by helping to control bleeding through aggregating and inducing clot formation in conjunction with blood coagulation factors. In healthy individuals, the average lifespan of platelets is 7 to 10 days, after which they are destroyed and replaced with newly generated platelets from the bone marrow. A normal blood platelet count ranges from $150\times10^9/L$ to $450\times10^9/L$, and patients who have less than $150\times10^9/L$ have the condition known as thrombocytopenia, which is associated with easy or excessive bruising and mild to severe or potentially fatal bleeding.

Thrombopoietin (TPO), the principal physiologic regulator of platelet production, is produced constitutively in the liver, circulates in the bloodstream, and is delivered to the bone marrow, where it stimulates the early development of multiple hematopoietic lineages leading to megakaryocytopoiesis. This results in the production of new platelets by the bone marrow, a process which is directly correlated with plasma TPO levels.

The circulating platelet count in the blood is determined by the rates of platelet production and platelet destruction. Thrombocytopenia can result from decreased platelet production in the bone marrow, increased platelet destruction in the blood (such as from autoantibodies), sequestration of platelets in the spleen, and/or the dilution of platelets following multiple blood transfusions. There are numerous disease states which cause thrombocytopenia, including immune thrombocytopenia (ITP), chronic liver disease (CLD), and chemotherapy-induced thrombocytopenia (CIT).

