1.3 Avatrombopag

Avatrombopag maleate is an orally administered, small molecule TPO-receptor (c-Mpl) agonist that mimics the biologic effects of TPO in vitro and in vivo, resulting in a measured increase in platelet counts. Like other TPO receptor agonists, avatrombopag activates the human TPO receptor, but binds to a different site on the receptor than endogenous TPO. After binding, avatrombopag stimulates signal transduction and mimics the biologic effects of TPO, which in turn increases platelet counts. Given its basic mechanism of action, by directly stimulating the normal production of new platelets by the bone marrow, avatrombopag has the potential to be useful for the treatment of thrombocytopenia of any etiology across a variety of indications and patient populations when used in both acute and chronic dosing regimens.

Avatrombopag has been approved by the US Food and Drug Administration (FDA) for the treatment of thrombocytopenia in adult patients with CLD who are scheduled to undergo a procedure and for the treatment of adult patients with chronic ITP who have had an insufficient response to a previous treatment (DOPTELET USPI).

Exposure to avatrombopag across the clinical development program includes chronic and acute dosing from a range of 1 to 100 mg. The total safety subject population from completed studies includes more than 1200 subjects who received avatrombopag and had at least 1 safety assessment. In the Phase 2 and 3 studies conducted in adults with ITP, avatrombopag was administered to 128 subjects for a median duration of 7 months and a maximum duration of 2.3 years. The primary efficacy endpoint in the pivotal Phase 3 ITP study (E5501-G000-302 [Study 302]) the Cumulative Number of Weeks with a platelet count \geq 50×10 9 /L during 6 months of treatment in the absence of rescue therapy, was a median of 12.4 weeks for avatrombopag versus 0 weeks for placebo (p<0.0001). The most common (\geq 10%) adverse events (AEs) in placebo and avatrombopag-treated subjects from the Phase 2 and 3 ITP studies (pooled data) are presented in Table 1.

Table 1 Adverse Events with a Frequency ≥10% in Subjects with Chronic ITP Treated with DOPTELET – Pooled Data from Clinical Trials^a

Adverse Event	DOPTELET (N=128)	Placebo (N=22)
Headache	31%	14%
Fatigue	28%	9%
Contusion	26%	18%
Epistaxis	19%	18%
Upper Respiratory Tract Infection	15%	5%
Arthralgia	13%	0%
Gingival Bleeding	13%	0%
Petechiae	11%	9%
Nasopharyngitis	10%	0%

a: DOPTELET USPI

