7.4 Treatment Period (through Day 90)

7.4.1 Day 15 (± 2 Days)/Visit 3

- Perform WHO Bleeding Scale Assessment (Appendix B). The Investigator should ask the subject the following question: "Have you had any bleeding or bruising since I saw you last?". This assessment should be completed prior to other visit assessments.
- Collect and record platelet count (local lab).
- Record the occurrence of any platelet transfusion (including the number of units).
- Record whether the subject required any rescue procedure for bleeding.
- Review subject Dosing Diary and record any deviations from prescribed dosing regimen in the eCRF.
- Record any changes in avatrombopag dose and dose frequency.
- Dispense additional avatrombopag to the subject, as needed.
- Record any data on Additional Safety Information (Section 9.1.1) or AESIs (Section 9.5) that have occurred.
- Record any AEs.
- Record any concomitant medication use, including concomitant ITP medications.
- Instruct subject on when to return for the Day 30 Visit.

7.4.2 Day 30 (± 2 Days)/Visit 4

- Administer TSQM Version 1.4 to the subject.
- Perform WHO Bleeding Scale Assessment (Appendix B). The Investigator should ask the subject the following question: "Have you had any bleeding or bruising since I saw you last?". This assessment should be completed prior to other visit assessments.
- Collect and record platelet count (local lab).

- Record the occurrence of any platelet transfusion (including the number of units).
- Record whether the subject required any rescue procedure for bleeding.
- Review subject Dosing Diary and record any deviations from prescribed dosing regimen in the eCRF.
- Record any changes in avatrombopag dose and dose frequency.
- Dispense additional avatrombopag to the subject, as needed.
- Record any data on Additional Safety Information (Section 9.1.1) or AESIs (Section 9.5) that have occurred.
- Record any AEs.
- Record any concomitant medication use, including concomitant ITP medications.
- Instruct subject on when to return for the Day 60 visit.

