10.2.2 Analysis of Platelet Count

Platelet count assessed at Baseline, Day 15, Day 30, Day 60, and Day 90 will be summarized descriptively for all enrolled subjects. Graphic presentations of platelet count over time will be provided.

The proportion of subjects who have a platelet count $\geq 50 \times 10^9 / L$ and $\leq 200 \times 10^9 / L$ will be tabulated using count and percentage for Baseline, Day 15, Day 30, Day 60, and Day 90.

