9.3 Other Safety Measures

9.3.1 Platelet Transfusions

[figure not shown]
A summary table will be created by prior TPO-RA (romiplostim and eltrombopag) and overall to display the frequency and percentage of enrolled subjects who have platelet transfusions (yes/no). The total number of platelet transfusions, and the reasons for transfusion (Thrombocytopenia, Bleeding Event, Adverse Event other than Bleeding Event, Other) will be summarized by category (subjects may appear in more than one category). The total number of packs/units received per transfusion will be summarized as a continuous variable.

Details of platelet transfusions occurring during the study will be presented in a listing.

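### The platelet endpoint counts visit values of 50 to 200 as in range even after a transfusion or a newly started ITP drug; a companion table should show how much this matters

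*SAP*

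**What the plan says.** SAP Section 3.2.2, like Protocol Section 3.2, lists as a secondary endpoint the "Proportion of subjects who have a platelet count between" 50 and 200 ×10⁹/L (both limits included) at Day 15, 30, 60 and 90. Protocol Section 10.2.2 says that the visit counts "will be summarized descriptively for all enrolled subjects. Graphic presentations of platelet count over time will be provided". SAP Section 8.2 says that the in-range proportion "will be tabulated using count and percentage for Baseline, Day 15, Day 30, Day 60, and Day 90". No passage makes the result depend on how the count was reached.

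The documents foresee treatments that raise the count. At each post-Baseline visit Protocol Section 7.4 tells the site: "Record the occurrence of any platelet transfusion (including the number of units"). It also asks for rescue procedures for bleeding and for concomitant ITP medications. SAP Section 9.3.1 summarises "the reasons for transfusion (Thrombocytopenia, Bleeding Event, Adverse Event other than Bleeding Event, Other"). SAP Section 7 plans tables of prior medications, of all concomitant medications, and of "Concomitant Medications taken as rescue for a bleeding event".

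**The concern.** The analysis sits in the efficacy/effectiveness section of the SAP, and Protocol Section 1.2 gives 50 to 200 ×10⁹/L as the range that ITP treatment aims for. Readers will take the proportion as platelet control on avatrombopag after the switch. Suppose a subject's count falls on avatrombopag, the subject is transfused or given another ITP drug, and the next visit count is 80. That visit is tabulated as in range. The study is single-arm and open-label, so no comparator would show how much of the proportion comes from added treatment.

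**Working it through.** **Is there a rule anywhere?**
- Endpoint and analysis text (Protocol 3.2, 10.2.2; SAP 3.2.2, 8.2): no condition.
- SAP 4.3.4: covers missing data only, with no imputation, and puts all available data into the tabulations.
- SAP 4.1.2: visit values are used under the visit label recorded in the eCRF, whatever the date.
- Protocol 5.1 and 5.2: no criterion bars concomitant ITP medication.
- Protocol 5.3.2: early termination may follow from investigator discretion, but starting another ITP drug is not itself a listed reason. Such a subject can stay on study and be counted.
- Protocol 7.4.5: the Day 90 visit is also the Early Termination visit, so a count taken after avatrombopag has stopped may be tabulated under Day 90.

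No passage supplies a rule.

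**Do the other tables repair it?** SAP 9.3.1 tabulates transfusions, SAP 7 tabulates medications, and SAP 8.2 lists counts by visit. A reader can see that rescue took place, but no table joins it to the in-range count. The rescue-medication table is limited to bleeding. An ITP drug added for a low count without bleeding appears only in the general concomitant table.

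**Is there a figure in the plan to reproduce?** Not for this endpoint. The only power figure is the 83% for TSQM convenience (n = 50, change 8, SD 19, two-sided 0.05). It reproduces at 83.1% and is not affected.

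**Size.** Let N be the number in the column, r the share with a recent transfusion or newly started ITP drug at a visit, and q the share of those whose count is 50 to 200. The proportion as written exceeds one that scores these visits as not in range by r × q.

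Per subject: 1/100 = 1 point overall and 1/50 = 2 points per prior-TPO-RA group. At the lower planned group size of 40 it is 1/40 = 2.5 points.

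The documents give neither r nor q. For assumed values with N = 100:

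| r | q = 0.5 | q = 1 |
|---|---|---|
| 0% | 0 | 0 |
| 2% | 1 point | 2 points |
| 5% | 2.5 points | 5 points |
| 10% | 5 points | 10 points |
| 15% | 7.5 points | 15 points |

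Illustration: an assumed 80/100 in range (Wilson 95% interval 71 to 87%) becomes 75/100 (66 to 83%) at r = 5%, q = 1. At r = 10%, q = 1 it becomes 70/100 (60 to 78%).

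**Direction.** If treatment is added for a count below 50 and lifts it into range, the proportion rises. But transfusion reasons in SAP 9.3.1 include bleeding and other events, so a subject already in range may be treated. If that takes the count above 200, the visit is scored out of range and the proportion falls.

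**The case against.** The objective is to evaluate platelet counts after the switch. A descriptive percentage of counts as observed under routine care answers it coherently. The endpoint is secondary, with no test and no success threshold, so no error rate or power is at stake. Subjects must have responded to a prior TPO-RA and been treated for at least 90 days, so rescue may be rare. Transfusions and medications are tabulated and listed, and Protocol Section 10.2.3 allows further platelet analyses. All of this stands. It limits the point to interpretation and argues for keeping the protocol-defined table. It does not supply the missing link, and an analysis chosen after the data are seen is weaker than one fixed beforehand.

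The documents do not support four stronger readings that a reader might infer:
- **The bias is always favourable.** The upper limit of 200 rules this out.
- **The plan dropped a safeguard.** Protocol Section 1.3 describes the pivotal study's endpoint as counted "during 6 months of treatment in the absence of rescue therapy". That was the primary endpoint, cumulative weeks, of a different, placebo-controlled study. This plan never adopted it. It shows only that such a condition is workable in this disease.
- **The overstatement is 6 to 10 points.** That needs 3 to 5 subjects per 50 who are both rescued near a visit and in range at it (3/50 = 6%, 5/50 = 10%). The documents give no such rate.
- **The protocol fixes a look-back of 10 days.** Protocol Section 1.1 does say that "the average lifespan of platelets is 7 to 10 days", but of healthy individuals. Section 1.2 describes increased platelet destruction in ITP. No source is given for a window after other ITP drugs either.

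**Conclusion.** The gap is real: both documents count post-transfusion and post-rescue values as in range, and nothing links rescue to those values. In a single-arm study this credits avatrombopag with counts that other treatment may have produced, mainly in the favourable direction. The effect is 1 point per affected in-range subject in 100 and 2 points in 50. The total is unknown: zero if nobody is treated near a visit, and about 1 to 15 points overall if 2 to 15% are and half to all of them are in range. Those rates are assumptions. This is an inexpensive improvement to how a descriptive secondary result can be read. It is not grounds for replacing the protocol's endpoint through an SAP edit.

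**What to change.** Keep the protocol-defined table in SAP Section 8.2. Before database lock, add a companion table by prior TPO-RA and overall. In it, score a visit as not in range if the count follows, within the look-back window, either:
- a platelet transfusion, or
- any ITP medication other than avatrombopag newly started after Day 1, including another TPO-RA and rescue given without bleeding.

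The sponsor should fix and justify the windows in advance. State the number of subjects affected at each visit, and how many of them were in range, and report the two proportions together.

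Costs and limits:
- One derived flag and one table.
- The companion proportion can only be equal or lower. It may understate control on avatrombopag where the count would have been in range anyway.
- The windows are conventions.
- Protocol Section 7.4 names the occurrence and units of on-study transfusions but not their date, so confirm that dates are captured.
- SAP Section 4.3.5 does not impute medication end dates, so a rule is needed for them. It sets a start date with a missing day to the first of the month, and one with missing day and month in the treatment-start year to the treatment start date. A drug started after Day 1 could then escape the flag, so partial start dates also need a rule.
- The table does not address carry-over from the prior TPO-RA, for which no washout is required.
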